5 RATIONALE AND BACKGROUND

Posaconazole¹, a triazole antifungal agent, is indicated for use in the treatment of the following invasive fungal infections (IFI) worldwide in patients with disease which is refractory to, or in patients who are intolerant of other alternative therapy: Aspergillosis, Candidiasis, Fusariosis, Zygomycosis, Cryptococcosis, Chromoblastomycosis, Mycetoma, and Coccidioidomycosis.

In China, NOXAFIL injection (for intravenous [IV] use) and tablet (for oral use) were approved on 30 Jan 2021 and 7 Dec 2018, respectively, for prophylaxis of invasive aspergillus and candida infections. Later, NOXAFIL injection and tablet, was approved for the treatment of invasive aspergillosis (IA) in adults on 29 Mar 2022.

In China, the current estimated prevalence of IA is around 1.17 million. [Zhou, L. H., et al 2020] The incidence rate of IA is rising. According to conservative estimates, China has reached 160,000 cases/year of IA in 2016. [Yuan, X. U., et al 2018]There are very few publications reporting the mortality of the Chinese national population. Existing literatures are outdated. A study reported the global mortality rate of IA is about 30-95% in 2012. [Brown, G. D., et al 2012]Studies from single site hospital in China reported the mortality rate of 39% among non-neutropenic patients with proven or probable IA and in a separate study, a mortality rate of 100% in among patients with a probable invasive pulmonary aspergillosis diagnosis admitted with HBV-related liver failure [Dai, Z., et al 2013] [Wang, W., et al 2011]. IA patients with underlying disease without timely treatment have the extremely high fatality rate.

Therefore, reduction in mortality among patients with IA is also a measure of real world effectiveness of antifungal treatment. All cause mortality (ACM) was a clinical endpoint in the Phase III study (MK5592-P069) of posaconazole vs. voriconazole for treatment of IA.

¹ The posaconazole mentioned in this protocol is the product of posaconazole injection and/or posaconazole tablets by Merck & Co., with the brand name 'Noxafil'

Rationale

The new injection and tablet formulations of posaconazole that are able to achieve a higher exposure target with reduced variability compared to posaconazole oral suspension. Noxafil (posaconazole) (MK-5592) injection and tablet has been approved by the National Medical Products Administration (NMPA) for the treatment of IA in adult patients on 29 Mar 2022.

	24

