7.2.2 Inclusion/Exclusion criteria for subjects receiving first line treatment

Inclusion criteria for subjects receiving first line treatment of IA:

- Chinese and resident in China;
- At least 18 years of age on the day of initiating posaconazole treatment;
- Diagnosed with proven, probable, possible IA per EORTC/MSGERC 2020 or 2021 EORTC/MSGERC-ICU criteria;
- Has received less than 7 days of other antifungal therapy with activity against aspergillosis (amphotericin, voriconazole, isavuconazole, or itraconazole) for treatment of the current episode of IA.

Exclusion criteria for subjects receiving first line treatment of IA:

- Unable to provide written informed consent if Ethics review committee (ERC) requires;
- Participating in any interventional clinical trial;
- Pregnancy or breast feeding during the treatment with posaconazole;
- Prior enrollment in current study (each subject may only be enrolled once);
- History or known aspergillus infection with a strain that is azole-resistance;
- Known or history of efficacy failure of posaconazole to treat a prior or current episode of IA.

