7.2.5.1 The Patients Identification Period

The patient identification period will be defined as the segment of time from date of posaconazole injection and tablet formulations has been approved by NMPA for the treatment of IA in adult patients (29 Mar 2022) until the planned last patients in date of the study. The whole identification period will last for about 32 months.

IA Patients who admitted to the selected hospitals and received at least 7 days of posaconazole (injection and/or tablet formulations) treatment (including monotherapy and combination^ therapy) during this period should be identified and observed. The procedures of how to identify eligible patients is presented in section 7.4.1.

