7.2.5.2 The Recruitment Period

The recruitment period will start after the leading site contract signed (Oct 2023 as planned) and plan to be ended by Dec 2024.

During this period, inclusion/exclusion criteria checking by treatment line should be carried on for patients who are identified and observed during the patients identification period. Qualified patients after inclusion/exclusion criteria check should be recruited into the study and followed up.

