7.2.5.4 Data Collection Period

This study involving both prospective and retrospective data collection.

The retrospective data collection period will be defined as date of posaconazole injection and tablet formulations has been approved by NMPA for the treatment of IA in adult patients (29 Mar 2022) until the start of recruitment period (Oct 2023 as planned).

The prospective data collection period will be defined as the start of recruitment period (Oct 2023 as planned) until the the planned patients last visit date of the study (Jan 2025).

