7.2.5.5 Patient Index Date and Specific Treatment Assessment Durations

Patient index date is defined as the date of the first treatment of posaconazole injection and/or tablet formulations.

	30
PRODUCT: MK5592	PROTOCOL/AMENDMENT VERSION NO.: 2
REVOPS ID NO: NIS102646	CORE DRC APPROVAL DATE: 18-SEP-2024
EPIDEMIOLOGY NO.(PE STUDIES ONLY): EP08047.004	

Specific treatment assessment duration for different outcomes are summarized as follows:

- Assessment for all-cause mortality for IA will occur at Day 42. Treatment may continue beyond Day 42.
- Assessment for overall response will occur at the end of treatment (for both first line and salvage treatment). Patients may continue treatment beyond 12 weeks (84 days) however assessment for response to therapy will occur at 84 days for such patients. For patients who receive less than 12 weeks of treatment, assessment will occur at the end of posaconazole treatment.

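### The exclusion for posaconazole efficacy failure in the current episode has no time anchor and, read literally, screens out patients in whom the evaluated course failed

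*Protocol*

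**What the plan says.** - **Criterion.** Protocol 7.2.2 (first line) excludes patients with "Known or history of efficacy failure of posaconazole to treat a prior or current episode of IA". Protocol 7.2.3 (salvage) repeats the same words. Efficacy failure is not defined in either list.
- **Neighbouring criteria.** Some do carry an anchor, for example "At least 18 years of age on the day of initiating posaconazole treatment". The first-line list also excludes "History or known aspergillus infection with a strain that is azole-resistance", again without a date.
- **Product.** Section 5, footnote 1: "The posaconazole mentioned in this protocol is the product of posaconazole injection and/or posaconazole tablets". These are the study exposure.
- **Index date.** Section 7.2.5.5: "Patient index date is defined as the date of the first treatment of posaconazole injection and/or tablet formulations".
- **Who is identified.** Section 7.2.5.1 picks up a patient only once a week or more of the sponsor's injection or tablets has been given, alone or with other antifungals.
- **When eligibility is checked.** Section 7.2.5.2, for the recruitment period planned from October 2023 to December 2024: "inclusion/exclusion criteria checking by treatment line should be carried on for patients who are identified and observed during the patients identification period". Retrospective data reach back to 29 March 2022 (7.2.5.4).
- **What is evaluated.** Section 7.1 says that, after the eligibility check, patients with response data enter the secondary analysis whether they succeeded or failed. Table 1 (7.3.2.2.1) puts stable response, progression and all-cause death under failure.

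**The concern.** An exclusion criterion should describe the patient at or before time zero. Time zero here is the first dose of the sponsor's injection or tablets, and the check takes place at least a week later, often after the course has ended. A failure of posaconazole in the current episode will therefore usually be a failure of the course being studied, which is the outcome itself.

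The study is single-arm and descriptive, with no hypothesis test (7.5). Its product is the mortality and response estimates, and no comparator shares the bias. Patients who are never enrolled cannot be recovered in the analysis. Section 7.10 discusses admission, survivor and missing-data bias, but not selection through this criterion.

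**Working it through.** **1. The plan's own precision figure.** Table 2 gives half-widths of 12.1 to 18.7 points for the two-sided exact (Clopper-Pearson) 95% interval. All ten rows reproduce. Examples: 6/40 gives 5.7 to 29.8, half-width 12.1; 12/40 gives 16.6 to 46.5, half-width 15.0; 15/30 gives 31.3 to 68.7, half-width 18.7. The stated precision is right. The issue is bias, which Table 2 cannot show.

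**2. The sections in time order.** First posaconazole treatment (index date, 7.2.5.5), then at least 7 days of treatment (7.2.5.1), then the eligibility check (7.2.5.2), then evaluation of successes and failures (7.1). A criterion on posaconazole failure in the current episode, applied at the third step with no date limit, can remove patients whom the fourth step is meant to count.

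**3. Size, as a scenario.** Let p be true Day 42 mortality, q the true ORR in a given denominator, r the share of patients who are retrospective, and f the share of their deaths (or failures, for ORR) removed by the criterion. Outcomes are assumed equal in the two strata.

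- Observed mortality = p(1 − rf) / (1 − rfp)
- Observed ORR = q / (1 − rf(1 − q))

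Of these inputs, only the range of p (15% to 50%, section 7.5) comes from the protocol; q, r and f are assumptions.

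With p = 0.30, q = 0.50, r = 0.5, f = 0.5:
- mortality = 0.30 × 0.75 / (1 − 0.075) = 0.225 / 0.925 = 24.3%
- ORR = 0.50 / (1 − 0.125) = 57.1%

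| r | f | Observed mortality (true 30%) | Observed ORR (true 50%) |
|---|---|---|---|
| any | 0 | 30.0% | 50.0% |
| 0.25 | 0.5 | 27.3% | 53.3% |
| 0.5 | 0.5 | 24.3% | 57.1% |
| 0.5 | 1 | 17.6% | 66.7% |
| 1 | 0.5 | 17.6% | 66.7% |

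The r = 1 row is the retrospective stratum taken alone. It matters because 7.8.1 and 7.8.2.1 stratify by method of data collection. At r = f = 0.5, a true mortality of 15% is observed as 11.7% and one of 50% as 42.9%; a true ORR of 40% becomes 47.1% and one of 60% becomes 66.7%.

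**4. Sensitivity of the mortality figure.** The mortality formula removes deaths only. If survivors with a failed response are removed too, the denominator shrinks and the shift is smaller. With 40 patients and 12 deaths, removing 3 deaths gives 9/37 = 24.3%; removing 3 deaths and 3 surviving failures gives 9/34 = 26.5%. Mortality falls only if the removed patients died more often than the cohort as a whole.

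**5. Which ORR.** ORR is reported by treatment line, and the first-line ORR covers patients treated for 42 to 84 days (7.1). The ORR formula must therefore be read within one line, with q and f defined for that line's own denominator. Day 42 deaths cannot simply be added to first-line failures.

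**The case against.** The strongest reply is that the rest of the protocol shows failures were meant to be counted. Section 7.1 evaluates them, Table 1 classifies them, and 7.3.2.2.3 records lack of response or progression as a reason for stopping posaconazole. If every failure on study were ineligible, those provisions would have little to record. Sites may well read the criterion as a baseline condition, and then nothing is lost. This stands as evidence of intent and makes the bias conditional. It does not supply the missing date, and it is itself one side of the contradiction.

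Four stronger readings are tempting but not supported:

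- **That failures are in fact being removed.** Nothing in the protocol shows how sites have applied the wording.
- **That failure in the current episode can only follow the index date.** A patient may have failed an earlier posaconazole course in the same episode and be on a second one. Section 7.2.5.5 does not say which course sets the index date in that case, so the reference to the current episode may have a legitimate use.
- **That deaths drop out in the same proportion as other failures.** Efficacy failure is undefined. If it means the failure category in Table 1, deaths are included. If it means non-response or progression only, mortality moves only through deaths that follow a recorded failure.
- **That the azole-resistance exclusion carries the same defect with equal force.** Its wording reads naturally as a baseline condition, and it stands in the first-line list only. Anchoring it is a matter of clarity.

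**Conclusion.** The point holds as a missing time anchor that puts 7.2.2 and 7.2.3 in conflict with 7.1 and Table 1. Applied as written, the criterion selects on the outcome. The ORR effect is upward and direct. The mortality effect is downward but depends on what counts as efficacy failure. Both are largest in the retrospective stratum, although a prospective patient screened after a failure is recorded can also be affected.

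The size cannot be known from the protocol. It is zero if all sites read the criterion as a baseline condition. At r = f = 0.5 the shift is 5.7 points in mortality (30% to 24.3%) and 7.1 points in ORR (50% to 57.1%), against a planned half-width for mortality of 15.0 points at 12/40. In the retrospective stratum alone, with half the deaths removed, the mortality shift is 12.4 points (30% to 17.6%). These are scenarios, not estimates.

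**What to change.** 1. In 7.2.2 and 7.2.3, limit the criterion to efficacy failure documented before the patient index date, and say that the index date is the start of the posaconazole course under evaluation. An earlier failed course, in a prior or the current episode, then remains a ground for exclusion.
2. State that failure during the evaluated course is an outcome and never a reason for exclusion, and reconcile the wording with 7.1 and Table 1.
3. For clarity, anchor the first-line azole-resistance exclusion to the same date.
4. Send sites a clarification, and review the screening log for every patient excluded on this criterion, re-admitting those whose failure arose during the evaluated course.

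The cost is small but not nil. Beyond the wording change, the letter and the log review, each re-admitted patient needs consent or an ethics waiver (7.4.1, 8.1), chart abstraction and, where vital status is missing, follow-up to Day 42 (7.4). Table 2 needs no change.

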7.2.3 Inclusion/Exclusion criteria for subjects receiving salvage treatment

Inclusion criteria for subjects receiving salvage treatment of IA:

- Chinese and resident of China;
- At least 18 years of age on the day of initiating posaconazole treatment;
- Diagnosis of probable, proven, possible IA per EORTC/MSGERC 2020 or 2021 EORTC/MSGERC-ICU criteria;
- Has a diagnosis of IA with disease that is refractory to amphotericin B, voriconazole, itraconazole, isavuconazole or other antifungal medicines with activity against Aspergillus. Refractoriness is defined as progression of infection or failure to improveafter the receipt of 7 or more days of these medicinal products for treatment of the current episode of infection;

PRODUCT: MK5592	PROTOCOL/AMENDMENT VERSION NO.: 2
REVOPS ID NO: NIS102646	CORE DRC APPROVAL DATE: 18-SEP-2024
EPIDEMIOLOGY NO.(PE STUDIES ONLY): EP08047.004	

- OR
- Has a diagnosis of IA in patients who have shown intolerance to amphotericin B, voriconazole, itraconazole, isavuconazole or other antifungal medicines with activity against Aspergillus after the receipt of 1 or more days of any of these medicinal products given for the treatment of the current episode of infections.

Exclusion criteria for subjects receiving salvage treatment of IA

- Unable to provide written informed consent if ERC requires;
- Participating in any interventional clinical trial;
- Pregnancy or breast feeding during the treatment with posaconazole;
- Prior enrollment into the study (each subject may only be enrolled once);
- Known or history of efficacy failure of posaconazole to treat a prior or current episode of IA.

7.2.4 Study Sites

Hospitals in which posaconazole injection and/or tablet is available and have the most patients using this product will be considered for inclusion in the study.

Site selection will depend on availability of posaconazole injections and/or tablets in hospitals, the potential eligible patient number, willingness of PI to participate, the completeness of medical records on study key information as well as the feasibility assessment from the operational perspective. The actual site numbers may be updated according to the actual execution.

7.2.5 Study Period

Figure 1 depicts the planned study period. The study period may be adjusted according to the actual enrollment of patients with available data to confirm the all-cause mortality through day 42 and overall response rate at the end of posaconazole treatment.

PRODUCT: MK5592	PROTOCOL/AMENDMENT VERSION NO.: 2
REVOPS ID NO: NIS102646	CORE DRC APPROVAL DATE: 18-SEP-2024
EPIDEMIOLOGY NO.(PE STUDIES ONLY): EP08047.004	

7.2.5.1 The Patients Identification Period

The patient identification period will be defined as the segment of time from date of posaconazole injection and tablet formulations has been approved by NMPA for the treatment of IA in adult patients (29 Mar 2022) until the planned last patients in date of the study. The whole identification period will last for about 32 months.

IA Patients who admitted to the selected hospitals and received at least 7 days of posaconazole (injection and/or tablet formulations) treatment (including monotherapy and combination^ therapy) during this period should be identified and observed. The procedures of how to identify eligible patients is presented in section 7.4.1.

7.2.5.2 The Recruitment Period

The recruitment period will start after the leading site contract signed (Oct 2023 as planned) and plan to be ended by Dec 2024.

During this period, inclusion/exclusion criteria checking by treatment line should be carried on for patients who are identified and observed during the patients identification period. Qualified patients after inclusion/exclusion criteria check should be recruited into the study and followed up.

7.2.5.3 The Follow up Period

According to treatment line different follow up period should be applied.

For patients who receiving first line treatment, a minimum follow up of 42 days and the maximum follow up of 84 days starting from the patient index date (see 7.2.5.5) are required.

For patients who receiving salvage treatment, a minimum follow up of 7 days and the maximum follow up of 84 days starting from the patient index date (see 7.2.5.5) are required.

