4 MILESTONES

Milestone	Planned Date
Registration in the EU PAS register	Within 35 days of protocol finalization in Regulatory Enterprise Document Source (REDS)
Start of data collection	Start date of data collection will be a date (planned Oct 2023) after Human Genetic Resource Administration of China (HGRAC) approval
End of data collection	Jan 2025 (planned date of last patient last visit)
Final report of study results	Jun 2025

PRODUCT: MK5592	PROTOCOL/AMENDMENT VERSION NO.: 2
REVOPS ID NO: NIS102646	CORE DRC APPROVAL DATE: 18-SEP-2024
EPIDEMIOLOGY NO.(PE STUDIES ONLY): EP08047.004	

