PRODUCT: MK5592	PROTOCOL/AMENDMENT VERSION NO.: 2
REVOPS ID NO: NIS102646	CORE DRC APPROVAL DATE: 18-SEP-2024
EPIDEMIOLOGY NO.(PE STUDIES ONLY): EP08047.004	

multicenter observational study prospectively and retrospectively collecting effectiveness information in Chinese adult IA patients with posaconazole.

The advantage of the observational study is to conduct the study without any intervention, which will obtain information on patients receiving posaconazole to better reflect real-world clinical practice. Currently, there is no database in China that can be used directly to assess the effectiveness of posaconazole. This study using medical records from multicenter as the basic data source is the most feasible research methods.

According to the evaluation of the number of IA patients in the potential research sites, extensiveness of prophylactic use and the enrollment difficulty and speed in clinical trial, the observed number of IA patients with posaconazole treatment in this study might be limited, hence this study proposed a combination of prospective and retrospective study design.

6 **RESEACH QUESTION AND OBJECTIVES**

The aim of this study is to assess all-cause mortality of posaconazole injection and/or tablet treatment of IA in Chinese adult patients by an observational study involving prospective and retrospective data from target hospitals using a case report form during the planned recruitment period (Oct 2023-Dec 2024).

6.1 **Primary Objective**

1. To assess all-cause mortality at day 42 of IA (proven, probable, possible) in Chinese adult patients who receive at least 7 days² of posaconazole injection and/or tablet formulations.

 2 Considering the real-world medication adherence of patients, in this study, if the prescribed duration of medication is specified and the actual duration of medication reaches 80% or more of the specified duration, it can be included in the analysis.

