7.2 Setting

7.2.1 Study Population

The overall study population will consist of IA adult Chinese patients (proven, probable, possible⁵) who received at least 7 days of posaconazole (injection and/or tablet formulations) treatment (including monotherapy and combination⁶ therapy) from Mar 2022 to Dec 2024 (planned date of last patient in).

⁵ Follow the definition of 2020 EORTC/MSGERC or 2021 EORTC/MSGERC-ICU consensus criteria [Donnelly, J. P., et al 2020] (see Annex 5).

⁶Combination therapy is defined as patient use posaconazole (injection and/or tablet formulations) with any other antifungal medications with activity against aspergillosis, medications used in as combination therapy should be recorded.

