7.3.2.1 Primary Outcomes

The primary outcome is all-cause death among proven, probable, possible IA patients who received at least 7 days of posaconazole injection and/or tablet formulations treatment through Day 42.

Death is defined as a patient with death is recorded in the medical history or death certificate can be provided through Day 42 or within Day 42. (Data cources see 7.4)

Patients with missing or 'unable to determine' dead or alive status through Day 42 will be excluded.

PRODUCT: MK5592	PROTOCOL/AMENDMENT VERSION NO.: 2
REVOPS ID NO: NIS102646	CORE DRC APPROVAL DATE: 18-SEP-2024
EPIDEMIOLOGY NO.(PE STUDIES ONLY): EP08047.004	

Secondary Outcomes 7.3.2.2

7.3.2.2.1 **Clinical response**

The clinical response of proven, probable, possible IA patients who received posaconazole injection and/or tablet formulations treatment as the first line or salvage treatment at the end of posaconazole treatment.

Clinical responses will be defined by using the 2017 Chinese guidelines for the diagnosis and treatment of invasive fungal disease in patients with hematological disorders and cancers (the fifth version) (Table 1) or by the investigator⁷(s).

⁷Considering the low compliance with guidelines in real-world clinical practice, it is possible that there may be insufficient information from medical record to support the definition of clinical response according to the guideline (Table 1). Therefore, investigator's professional judgment could be used to define the clinical response. The subgroup analysis by the methods of clinical response definition (guideline vs. investigator's professional judgment) will be conducted depending on data availability. (see 7.7.2.1)

See Table 1 for the definitions for clinical response from the 2017 Chinese guidelines for the diagnosis and treatment of invasive fungal disease in patients with hematological disorders and cancers (the fifth version). The Chinese guidelines are consistent with the 2008 EORTC/MSG guidelines.

Table 1 Clinical Response Definitions from the 2017 Chinese guidelines for the diagisnos and treatment of invasive fungal disease in patients with hematological disorders and cancers (the fifth version).

Outcome, Response	Criteria
Success	

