7.8 Data Analysis

A descriptive analysis of the distribution of values abstracted for each variable will be provided. For the continuous variables we are interested, the values of mean/median, standard deviation (SD), min/max, interquartile range (IQR, including the first quartile [Q1] and third quartile [Q3]) will be calculated; the frequency and percentages will be calculated for these categorical variables. All analyses will be carried out using all available data. A participant with missing data on one variable will be used only in calculations that do not involve that variable.

	39
PRODUCT: MK5592	PROTOCOL/AMENDMENT VERSION NO.: 2
REVOPS ID NO: NIS102646	CORE DRC APPROVAL DATE: 18-SEP-2024
EPIDEMIOLOGY NO.(PE STUDIES ONLY): EP08047.004	

All analyses will use SAS (SAS Institute Inc., Cary, North Carolina). Detailed statistical analysis plan (SAP) and corresponding mock-up tables/figures/listings will be described separately prior to the commencement of any analyses.

All analysis detailed will be described in a separate "Statistical Analysis Plan". Key points are listed below.

7.8.1 **Primary Objective**

The primary objective is to assess the all-cause mortality of using posaconazole for proven, probable, possible IA patients. The all-cause mortality will be calculated with 95% CI.

Total all-cause mortality=number of total IA patients who die through Day 42/number of all IA patients (proven, probable, possible) included in the study with dead or alive status reported x 100%.

All-cause mortality by treatment line=number of IA patients by treatment line who die through Day 42/number of IA patients by treatment line (proven, probable, possible) included in the study with dead or alive status reported x 100%.

The analysis will be stratified by method of data collection: prospective vs. retrospective.

The following subgroupanalysis may be conducted depending on data availability:

- 1. Treatment duration (e.g. group by median treatment duration, etc);
- 2. Patients who only receive Posaconazole injection vs patients who receive Posaconazole injection then Posaconazole tablet;
- 3. Risk factors for mortality and poor outcome (Allogeneic hematopoietic stem cell transplant (HSCT); Relapsed leukemia, undergoing salvage chemotherapy; Liver transplant recipients)
- 4. IA at sites: Pulmonary IA vs others (sinus/upper respiratory involvement or disseminated disease to other organs).

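### The 7-day follow-up minimum for salvage patients and the January 2025 last visit do not reach the Day-42 and Day-84 assessments

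*Protocol*

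**What the plan says.** Section 7.2.5.3 sets follow-up by treatment line, counted from the first posaconazole dose.

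- First line: "For patients who receiving first line treatment, a minimum follow up of 42 days and the maximum follow up of 84 days".
- Salvage: "For patients who receiving salvage treatment, a minimum follow up of 7 days and the maximum follow up of 84 days".

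The primary objective in 6.1 has no restriction by line: "To assess all-cause mortality at day 42 of IA (proven, probable, possible) in Chinese adult patients who receive at least 7 days" of posaconazole. Section 7.8.1 reports the endpoint in total and again by line: "All-cause mortality by treatment line=number of IA patients by treatment line who die through Day 42". The amendment table in Section 3 lists the sections changed when the restriction to first-line patients was lifted. Section 7.2.5.3 is not among them.

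On missing status, 7.3.2.1 says: "Patients with missing or 'unable to determine' dead or alive status through Day 42 will be excluded". Section 7.3.2.2.1 treats missing response in the same way.

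On the calendar, 7.2.1 takes patients treated "from Mar 2022 to Dec 2024 (planned date of last patient in"), and Section 4 ends data collection in "Jan 2025 (planned date of last patient last visit").

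**The concern.** The first-line minimum of 42 days reaches the primary time point. The salvage minimum does not. A site that follows a prospective salvage patient for 7 days has complied with 7.2.5.3 and may still deliver no primary outcome.

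The loss depends on outcome. A death on Day 20 that is in the record counts in numerator and denominator. A patient last seen alive on Day 10 leaves the denominator. Mortality then rises, and it rises in one line only. That matters because 7.10 relies on reporting by line to deal with sicker patients at top-level hospitals.

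The calendar raises a second problem of the same kind. Patients who start late in 2024 reach Day 42, or Day 84 if still on treatment, after the planned last visit.

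**Working it through.** **The plan's own precision figure.** Table 2 gives two-sided exact 95% intervals for 15% to 50% mortality with 30 to 40 patients. All ten rows reproduce. For example, 6/40 gives 5.7% to 29.8% (half-width 12.1) and 15/30 gives 31.3% to 68.7% (half-width 18.7). At 30% mortality the half-width is 17.3 points with 30 patients and 15.0 with 40.

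**Is there a Day-42 duty for salvage patients elsewhere?**

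| Section | What it does | Binds a prospective salvage patient to Day 42? |
|---|---|---|
| 7.1 | Makes Day-42 status a condition of primary evaluation | No, it selects patients |
| 7.2.5.5 | Times the mortality assessment at Day 42 | It implies the need but sets no follow-up length |
| 7.4 | Requires tracing to Day 42 where status is missing | No, retrospective cases only |
| 7.10 | Promises monitoring of prospective cases | No duration stated |

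**Effect of losing survivors.** Let p be true mortality and f the fraction of survivors without Day-42 status, with all deaths kept. Observed mortality = p / [p + (1 − p)(1 − f)]. The protocol gives no f, so 10% and 30% are assumptions.

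- p = 15%: 0.15/0.915 = 16.4%; 0.15/0.745 = 20.1%.
- p = 30%: 0.30/0.93 = 32.3%; 0.30/0.79 = 38.0%.
- p = 50%: 0.50/0.95 = 52.6%; 0.50/0.85 = 58.8%.

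The formula applies within the salvage line or overall. Overall, f is smaller than within salvage if only salvage patients are lost.

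**Calendar.** From 31 December 2024 to 31 January 2025 is 31 days, less than the 42 days that 7.2.5.3 itself requires for first line. The latest start that allows 7 treatment days by 31 December is 25 December. It reaches Day 42 on about 5 February 2025 and Day 84 on about 19 March 2025. The protocol names only the month of the last visit, so the latest index dates covered are:

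| Last visit | Day 42 reached for index to about | Day 84 reached for index to about |
|---|---|---|
| 31 January 2025 | 20 December 2024 | 8 November 2024 |
| 15 January 2025 | 4 December 2024 | 23 October 2024 |
| 1 January 2025 | 20 November 2024 | 9 October 2024 |

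**How many patients.** The protocol gives no accrual pattern. Assume uniform index dates from 29 March 2022 to 25 December 2024 (1003 days) and 55 to 70 patients.

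- Day 42: 5/1003 = 0.5%, about 0.3 patients (31 January visit), to 35/1003 = 3.5%, about 2 patients (1 January visit).
- Day 84: 47/1003 = 4.7% to 77/1003 = 7.7%, about 3 to 5 patients, relevant only if still on treatment.

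If accrual is mainly prospective, these shares roughly double.

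**The case against.** Seven days is a floor with a ceiling of 84, and 7.1 and 7.2.5.5 plainly expect Day-42 status. Section 7.4 makes tracing mandatory for retrospective cases, and 7.10 adds contact with relatives for them. A reader might infer that salvage survivors will lack status and be excluded. The protocol does not support that: it permits the loss, for prospective salvage patients, and does not prescribe it.

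On the calendar, 7.2.5.1 puts identification at about 32 months, which ends about 29 November 2024. That start reaches Day 42 on about 10 January 2025. Section 7.2.5 also allows the study period to be adjusted. Because follow-up runs from first dose, patients treated earlier but recruited late have already passed both time points. All of this stands and makes the Day-42 calendar gap small. It does not close the Day-84 gap, since 29 November plus 84 days is about 21 February 2025, and the permission to adjust fixes no date.

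A reader might also infer that the response rate is understated. That is not shown. Response is assessed at end of treatment, and Day 84 applies only to patients still on drug then. The 7-day salvage minimum matches the salvage treatment minimum for that endpoint. First-line patients treated for under 42 days are outside the response set under 7.1. Early successes who stop are counted, and patients still on treatment may turn out either way.

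**Conclusion.** The point holds as an inconsistency to reconcile, and it should be fixed. The salvage minimum is the more important part because it bears on the primary endpoint, but its effect cannot be sized from the protocol. If 10% to 30% of survivors were lost, a true 30% would read 2.3 to 8.0 points too high, against a half-width of 15.0 to 17.3 points that does not reflect this bias. The upward direction assumes that deaths through Day 42 reach the record. A death after contact ends that nobody records would also be excluded and would weaken the effect.

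The calendar part is real but small for Day 42 (about 0.3 to 2 patients) and modest for Day 84 (about 3 to 5, only if still on treatment), both under assumed uniform accrual. The direction of any bias in the response rate is not established. Neither part supports saying that the primary endpoint cannot be measured.

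**What to change.** 1. In 7.2.5.3, require vital-status ascertainment to Day 42 for every patient, regardless of treatment line or stopping of posaconazole. Keep response assessment at end of treatment or Day 84, as in 7.2.5.5.
2. Then do one of the following:
   - move the last visit and end of data collection to about the end of March 2025 (an index date of 31 December 2024 reaches Day 84 on 25 March), leaving the final report in June 2025; or
   - set a last index date at least 84 days before the last visit, or 42 days for patients counted only for mortality.

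Cost: amendment wording, one status contact per salvage patient who stops early, and either a data cut about two months later or a few late patients forgone.
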